7.1. Primary Efficacy Analyses

7.1.1. Endpoint / Variables

The time to the first SFI flare over 52 weeks will be estimated for the treatment groups using the product-limit method.

Analyses of SFI flare (defined as mild, moderate, or severe) will be performed on the SELENA SLEDAI SLE flare index. Note: Flares in this study are analysed using the modified SLE flare index where severe flares that are triggered only by an increase in SELENA SLEDAI score to greater than 12 are not categorized as severe in the analysis.

7.1.2. Summary Measure

Only post-baseline flares will be considered in these analyses. Flares (not subjects) occurring on the Day 0 visit date should be removed from the analysis set prior to determining the first flare.

Data observed at or prior to the baseline visit (see Section 5.3.1) will not be included in this analysis.

Time to first SFI flare is defined as the number of days from baseline date (see Section 5.3.1) to the date the subject has a flare (event date – baseline visit date + 1).

See Section. 13.6.3 for additional details.

7.1.3. Population of Interest

The primary efficacy analyses will be based on ITT population.

7.1.4. Strategy for Intercurrent (Post-Randomization) Events

The disposition of subjects as it relates to intercurrent events is defined as follows:

	Event				
Subject Disposition	Met	Event Date [2]			
Subject has a SFI flare or takes a prohibited medication					
Subject has a SFI flare during the study	Yes	Date of first SFI flare			
[1]					
Subject takes a prohibited medication [1]	Yes	Date of prohibited medication			
Subject does not have a SFI flare and did not take a prohibited medication.					
Subject withdraws from the study or is	No	Censored at last available date where			
lost to follow-up		flare is assessed.			
Subject dies during the study	No	Censored at date of death.			

Subject completes the study	No	Censored at last study visit where flare is
		assessed.

[1] If a subject has a SFI flare and takes a prohibited medication, the event date is the earliest of the first SFI flare date and takes a prohibited medication date.

[2] If a subject meets multiple criteria, then the event date is the earliest date.

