8.1.2. Primary Efficacy Analysis

Time to first SLE flare will be analyzed using a time-to-event analysis. Time to first SLE flare is defined as the number of days from Day 0 of the BEL116027 study to the first occurrence of a SLE flare. If a subject withdraws from the study or completes week 52 without a SLE flare, time to the first SLE flare will be censored at the time of the last observation (last visit measuring flare). However, if a subject receives prohibited medication during the study, the subject will be considered as having a SLE flare at the time the medication is started. Data observed at or prior to the Day 0 visit will not be included in this analysis.

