13.6.3. Efficacy

SLE Flares and Severe Flares, and Renal Flares

Baseline Flares

• Baseline flares will be summarized using the data from the eCRF SFI data collection for the Day 0 visit. Per eCRF completion guidelines, the data collected at the Day 0 visit represents the flare data since the previous visit (i.e. the last visit in the feeder continuation study).

SLE Flares and Severe SLE Flares

2018N381035_00 BEL116027

SLE Flares and Severe Flares, and Renal Flares
CCI - This section contained Clinical Outcome Assessment data collection questionnaires or indices, which are protected by third party copyright laws and therefore have been excluded.

- SFI reports the first mild /moderate or severe flare occurrence since the last visit assessment.
- The SLEDAI criteria will be assessed programmatically to determine if the SELENA SLEDAI criteria for a flare has been met and used for the assessment of flare, irrespective of what was recorded on the SFI form.
- Although there are boxes on the form for the investigator to classify the most recent flare to mild/moderate or severe, the classification will be re-derived from the subcategory scores. Flares originally marked severe will be downgraded to "Not Severe" if the only reason marked is a change in SELENA SLEDAI score to > 12.
- In this case, if any of the mild/moderate reasons are checked or if the modified SELENA SLEDAI score has a change from previous visit of at least 3, then the flare will be considered Mild/Moderate.
- Flares that are marked mild/moderate where the only reason checked is SELENA SLEDAI increase of at least 3 points but not more than 12 points will be re-derived using the modified SELENA SLEDAI score.
- If it's found that the change is not actually ≥ 3 , and no other reasons are checked,

SLE Flares and Severe Flares, and Renal Flares

then the flare will not be counted.

Renal Flares

A SLE Renal flare is defined as the occurrence of at least 1 or more of the following in 2 or more consecutive visits during the study. (NB: at least 1 of the same criteria must be present on at least 2 consecutive visits)

Increased Proteinuria (using spot urine)

A reproducible increase in 24-hour urine protein levels (as measured in uPCR) to:

```
• >1g if the baseline (Day 0)value was <0.2g
```

OR

• >2g if the baseline (Day 0) value was between 0.2g and 1g

OR

• More than twice the value at baseline (Day 0) if the baseline value (Day 0)was >1g

Impaired Renal Function

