13.7.2.1. Handling of Missing and Partial Dates

Element	Reporting Detail				
General	Partial dates will be displayed as captured in subject listing displays.				
Adverse Events	 The eCRF allows for the possibility of partial dates (i.e., only month and year) to be recorded for AE start and end dates; that is, the day of the month may be missing. In such a case, the following conventions will be applied for calculating the time to onset and the duration of the event: Missing Start Day: First of the month will be used unless this is before the start date of study treatment; in this case the Day 0 visit date (LTD and TH arms) or the study treatment start date (TC arm) will be used and hence the event is considered On-treatment as per Appendix 4: Study Phases and Treatment Emergent Adverse Events. Missing Stop Day: Last day of the month will be used, unless this is after the stop date of study treatment; in this case the study treatment stop date will be used. 				
	• Completely missing start or end dates will remain missing, with no imputation applied. Consequently, time to onset and duration of such events will be missing.				
Concomitant Medications and Medical History	• Medications with partial or missing start and/or stop dates will be assumed to be concomitant unless there is evidence through comparison of partial dates to suggest otherwise, for example if the day is missing, then the month and year will be compared to the month and year of the first dose date of study treatment and if the month and year are the same or later, then the medication will be considered concomitant.				

Element	Reporting Detail
Time to SFI	Evaluated up to Week 52
Flares	 If a subject takes a prohibited medication during the time period being analyzed, the subject will be considered as having a SFI flare at the start date of the prohibited medication.
	 If a subject withdraws from the study, the will be censored at last flare assessment date
	 If a subject dies, censor at the date of death
Time to Renal	Evaluated up to Week 52
Flare	• If a subject withdraws from the study, the will be censored at last renal flare assessment date
	If a subject dies, censor at the date of death
Number of SFI Flares	• If a subject withdraws from the study, dies or takes a prohibited medication, the subject will be considered as having a SFI flare.

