13.9.10.5. Fatalities

All fatalities will be identified in the clinical database and subsequently adjudicated by the GSK SRT into a general category of death.

All fatalities will be adjudicated into one of the following categories:

Adjudicated Category of Death
SLE-Related
Infectious
Vascular
Gastrointestinal
Respiratory
Malignancy
Hypersensitivity
Suicide
Surgical Complication
Unknown
Hematologic
Trauma

Additional 'categories of death' may be added in the future should a fatality not clearly fit into one of the 'categories' listed above. The 'categories' will not change unless agreed upon by the GSK SRT.

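### Deaths without an earlier recorded flare are censored as flare-free at the date of death, even when SLE-related, and SAP 7.2.4.1 conflicts with that rule

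*SAP*

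**What the plan says.** SAP 7.1.4 sets out how intercurrent events enter the primary endpoint. A first SFI flare or the start of a prohibited medication is an event on its own date. The remaining rows fall under a sub-heading that limits them: "Subject does not have a SFI flare and did not take a prohibited medication". Within that block, withdrawn or lost subjects and completers are censored at the last date or visit with a flare assessment, while a subject who dies is "Censored at date of death". A footnote adds: "If a subject meets multiple criteria, then the event date is the earliest date".

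SAP Appendix 7 repeats the rule in its Time to SFI Flares row. That table belongs to 13.7.3; in the text as read it stands just above the 13.7.3 heading. A withdrawn subject is "censored at last flare assessment date", but "If a subject dies, censor at the date of death".

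Protocol 8.1.2 gives one censoring date, for subjects who withdraw or complete Week 52 without a flare: "time to the first SLE flare will be censored at the time of the last observation (last visit measuring flare". It has no separate rule for death. SAP Table 2, which lists departures from the protocol's analysis plan, does not mention one.

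Three other places bear on the point:

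- **Capture of flares.** SAP 13.6.3: "SFI reports the first mild /moderate or severe flare occurrence since the last visit assessment".
- **Cause of death.** SAP 13.9.10.5: "All fatalities will be adjudicated into one of the following categories". The first category is SLE-Related. The primary endpoint makes no use of it.
- **Secondary flare endpoints.** SAP 7.2.4.1, whose heading covers both the rate of flares and the first severe SFI flare, refers back to 7.1.4. It then says that a subject who withdraws, dies or takes a prohibited medication is considered to have had a SFI flare. Appendix 7 attaches that rule only to the number of SFI flares.

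**The concern.** Product-limit censoring assumes that a censored subject had the same future flare risk as those still under observation. That is not credible for someone who has just died of lupus. The plan already accepts a clinical proxy for flare, since starting a prohibited medication is an event. An adjudicated SLE-related death is stronger evidence of worsening disease, yet it enters as flare-free follow-up.

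The censoring date is a second, smaller matter. Because the SFI looks back from a visit, flare status after the last visit is unknown, and death is the only row that credits that time as flare-free.

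The third matter is internal consistency. If the second sentence of 7.2.4.1 applies to first severe flare, one death could be an event there and a censored observation for first flare of any severity, although severe flares are a subset of all flares. That sentence also gives no date and no severity for the imputed flare. A programmer cannot resolve this from the text.

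**Working it through.** The study is descriptive and gives no power or event calculation to reproduce. The enrolled numbers in SAP 2.3 do add up: 12 + 29 + 39 = 80.

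**1. Unassessed time.** Visits are every 4 weeks with a window of ±7 days. If no visit is missed, the time credited after the last assessment is at most 28 days nominally, and 28 + 7 + 7 = 42 days at the window edges.

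**2. Hand example, n = 12.** Suppose flares on days 60, 90, 120 and 200, and a death on day 150.

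- As written: S = (11/12)(10/11)(9/10)(7/8) = 0.656, a 52-week flare estimate of 34.4%.
- Death counted as an event: S = 7/12 = 0.583, an estimate of 41.7%.
- The median is not reached under either coding, since both values of S exceed 0.5.

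**3. Range over scenarios.** Assumptions: one flare-free subject per group dies 27 days after the last assessment (assessed day 85, 169 or 309; death day 112, 196 or 336). The other subjects have exponential flare times with a 52-week flare proportion of 57.5%, 67.4%, 74.6% or 81.5%, all values in the pooled BLISS table in SAP section 2. Changes in the 52-week estimate, relative to censoring at death:

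| Group | Death as event | Censored at last assessment |
|---|---|---|
| Holiday, n = 12 | +2.4 to +8.3 points | 0 to +2.8 points |
| Control, n = 29 | +1.0 to +3.2 points | +0.1 to +0.4 points |
| Long-term discontinuation, n = 39 | +0.8 to +2.4 points | +0.1 to +0.2 points |

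The holiday-group limits can be checked by hand. The smallest event effect is 10/12 − 17/21 = 0.024 (81.5%, death on day 112). The largest is 1/12 = 0.083, when the death follows the last flare. The largest date effect is 7/9 − 3/4 = 0.028 (81.5%, death on day 336). Subtracting percentages already rounded to one decimal gives 2.3 to 8.4 instead of 2.4 to 8.3.

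Counting the death as an event can also shorten the median: with n = 12, a 67.4% flare proportion and death on day 112, it falls from 226 to 171 days. Moving only the censoring date changes no median in these scenarios.

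**4. How often it might matter.** The documents give no death count. Protocol 1.1 puts 20-year survival from diagnosis at about 70%. At a constant hazard (an assumption) that is −ln(0.70)/20 = 0.0178 per year. Over one year this gives 80 × 0.0178 = 1.4 deaths of any cause overall and 12 × 0.0178 = 0.2 in the holiday group. If mortality here is a quarter to a half of that, the overall figure is 0.4 to 0.7. Only deaths that are SLE-related, with no earlier flare and no prohibited therapy, are affected by the event coding, so the relevant number is a fraction of these.

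**The case against.** The strongest defence is that the gap is narrow. The death row covers only subjects with no earlier flare and no prohibited medication. Protocol 6.3.1.3 makes hospitalization for SLE activity a severe-flare category. Protocol 5.5.2 prohibits IV cyclophosphamide, IVIG and plasmapheresis, so starting one of these is an event. Many fatal flares would be counted by one of these routes. All of this stands. A reader might infer that every death is censored, or that a fatal flare between visits can never be an event; the text supports neither. The documents also do not say whether an SFI entry can be made after a death between visits, and part of the flare derivation is withheld.

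A reader might also infer that the primary rule carries straight over to first severe flare, so that a lone SLE death leaves that estimate at 0% when it could be 1/12 = 8.3%. The documents do not support this as fact, because 7.2.4.1 goes on to count a death as a SFI flare. What can be said is that the SAP contradicts itself there.

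Three further points have weight. Protocol 8.1.2 does not mention death, so the SAP may be filling a gap; the accurate description is an unlisted departure from the only censoring date the protocol gives. The SAP's earliest-date footnote might pull the date back to the last assessment if a death is also coded as a withdrawal, but the SAP does not settle this. Finally, an SLE-related death is a sponsor adjudication made for reporting purposes, not an SFI flare. The SAP already reports 80 enrolled and refers to the last patient's last visit, so this would be a late change to a primary event in an open-label study. That calls for open documentation, but it does not make flare-free censoring of a lupus death a better description.

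**Conclusion.** The point holds in limited form. A death with no earlier recorded flare or prohibited medication is censored as a non-event at the date of death even if adjudicated SLE-Related. The date differs from every other censoring row for this endpoint and from Protocol 8.1.2, and the difference is not listed. SAP 7.2.4.1 leaves the treatment of deaths in first severe flare unresolved.

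The event coding matters more than the date: in the 12-subject holiday group, 2.4 to 8.3 points per assumed death against 0 to 2.8. These figures rest on one assumed death, exponential flare times and the pooled BLISS flare proportions. Without deaths there is no numerical effect, though the contradiction in the text remains. The results are descriptive, so no error rate or test is affected. The change is worth making because it concerns the primary endpoint in a very small group and needs little work.

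**What to change.** Before database freeze, amend SAP 7.1.4 and the Time to SFI Flares row of 13.7.3 by replacing the death rule with two rules:

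- (a) A death adjudicated SLE-Related, without an earlier counted flare, is an event on the date of death.
- (b) Any other death is censored at the last visit where flare was assessed, as in Protocol 8.1.2.

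Reword 7.2.4.1 so that first severe flare follows the same death rule. Keep death-as-flare, if it is wanted, for the number of flares only. List the change in Table 2, and say there that it was made after enrolment had closed.

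The cost is a few lines of SAP text and one derivation. SAP 13.9.10 already requires the adjudication before database release. The downsides are that flare estimates become slightly less favourable if an SLE-related death occurs, and that the primary event then includes a sponsor-adjudicated component.

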7.1.5. Statistical Analyses / Methods

Details of the planned displays are provided in Appendix 11: List of Data Displays and will be based on GSK data standards and statistical principles.

Unless otherwise specified, endpoints / variables defined in Section 7.1.1 will be summarised using descriptive statistics, graphically presented (where appropriate) and listed.

The table will display the number and percentage of subjects with a SFI flare, as well as the median, 25th, and 75th percentile of days to first SFI flare, estimated using the product-limit method. For subjects who experience a SFI flare, the study day of the SFI flare will be summarized and the table will display the median, 25th and 75th percentiles and minimum and maximum.

A cumulative incidence curve for time to first SFI flare will also be produced for the 52week treatment phase.

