2. OBJECTIVE(S)

2.1. Primary Objective

Characterize the efficacy of a 24-week withdrawal followed by a 28-week reintroduction of intravenous belimumab therapy compared with uninterrupted intravenous belimumab therapy for 52 weeks in subjects with low SLE disease activity receiving belimumab 10 mg/kg plus standard of care, as measured by time to first flare.

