8. DATA ANALYSIS AND STATISTICAL CONSIDERATIONS

Originally a total of approximately 135 subjects (50 in the treatment holiday group, 50 in the control group, and 35 in the long term discontinuation group) were planned to be enrolled in this study. After 36 months had elapsed since study start, a reduction in sample size was agreed to with regulatory authorities, and a total of at least 71 patients (at least 10 in treatment holiday, at least 26 in the control group and 35 in the long term discontinuation group) will be the target sample size to be enrolled in this study. The total sample size is based on practical considerations on the availability of subjects from other ongoing belimumab studies, rather than on statistical considerations. Since this is a non-randomized study, results will be descriptive only, and not intended to be inferential. No power calculations were made in the determination of sample size for this study. However, the total of subjects is expected to provide adequate information to characterize time to SLE flare. Table 4 shows the flare rates for the pooled BLISS studies.

ISE Table	Analysis	Placebo	1 mg/kg	10 mg/kg
Т57	Percentage of Subjects with Flare Over 52 Weeks	81.5%	74.6%	74.6%
TAC411	Percentage of Subjects with Flare Over 52 Weeks Post Week 24	68.5%	54.7%	57.5%
TAC613	Percentage of Subjects with Flare Over 52 Weeks Among SRI Wk 52 Responders	73.4%	69.8%	67.4%

Table 4 Flare Rates from Pooled BLISS Studies

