13.11.5. Efficacy Tables

Efficacy	: Tables			
No.	Population	Title	Programming Notes	Priority Headline Results denoted by H
Flares				
2.1.	ITT	Time to First SFI Flare to Week 52	Primary endpoint	Н
2.2.	ITT	SFI Flares per Subject-year from Day 0 to Week 52	Secondary endpoint	
2.3.	ITT	Time to First SFI Severe Flare to Week 52	Secondary endpoint	Н
2.4.	ITT	Time to First Renal Flare to Week 52	Exploratory endpoint	Н
2.5.	ITT	Time to First Renal Flare to Week 52 [1] Among Subjects with Baseline Proteinuria >0.5g/24hr Equivalent	Exploratory endpoint	
Reboun	d and SELENA-	SLEDAI		
2.6.	ITT	SELENA SLEDAI Rebound (LOCF) (52-Week Treatment Phase)	Secondary endpoint	Н
2.7.	ITT	SELENA SLEDAI Change from Baseline (LOCF) (52-Week Treatment Phase)	Secondary endpoint	
PGA		·		
2.8.	ITT	PGA Change from Baseline (52-Week Treatment Phase)	Other/exploratory endpoint	
Prednis	one			
2.9.	ITT	Number of Days of Daily Prednisone Dose >=7.5 mg/day and/or Increased by 25%	Secondary endpoint	
2.10.	ITT	Number of Days of Daily Prednisone Dose <=7.5 mg/day and/or Decreased by 25%	Secondary endpoint	

Efficacy	Efficacy: Tables				
No.	Population	Title	Programming Notes	Priority Headline Results denoted by H	
2.11.	ITT	Prednisone Percent Change from Baseline (52-Week Treatment Phase)	Other/exploratory endpoint		
2.12.	ITT	Prednisone Reduced to <= 7.5 mg/day by Visit (DO/TF=NR) among Subjects with Baseline Prednisone Dose > 7.5 mg/day (52-Week Treatment Phase)	Other/exploratory endpoint		

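### Headline Table 2.1 prints a flarers-only study day and a crude flare percentage, neither of which supports the holiday-versus-control comparison, and no product-limit flare probability is tabulated

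*SAP*

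**What the plan says.** The primary objective (Protocol 2.1) compares a belimumab holiday with uninterrupted therapy, "as measured by time to first flare". Protocol 8 sets no power target but states that "the total of subjects is expected to provide adequate information to characterize time to SLE flare".

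SAP 7.1.5 specifies three items for the primary table:

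- a count and percentage: "The table will display the number and percentage of subjects with a SFI flare";
- the median and quartiles from the product-limit fit: "percentile of days to first SFI flare, estimated using the product-limit method";
- a conditional summary (median, quartiles, minimum, maximum): "For subjects who experience a SFI flare, the study day of the SFI flare will be summarized".

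It also plans a figure: "A cumulative incidence curve for time to first SFI flare will also be produced". The table and figure are both titled "Time to First SFI Flare to Week 52" and both are marked as headline results (SAP 13.11.5 and 13.11.6).

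In the primary analysis a withdrawal or death without a flare is a censored non-event (SAP 7.1.4). For withdrawal, SAP 13.7.2.1 repeats the rule: "If a subject withdraws from the study, the will be censored at last flare assessment date". SAP 7.1.5 does not name the denominator of the percentage; since SAP 7.1.3 bases the analysis on the ITT population, the natural reading is the ITT group size. No product-limit probability at a fixed week is listed.

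The opening of SAP 7 says that efficacy results for the holiday group are shown separately for the holiday and re-start phases. The title of Table 2.1 runs to Week 52.

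**The concern.** The flarers-only summary drops every subject who stayed flare-free. It describes when flares happen among those who have one within the window. That depends heavily on the window's length and only weakly on flare risk, and a difference in flare risk is what the objective asks about.

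The crude percentage treats a subject censored early as flare-free to Week 52. It equals the 52-week risk only if nobody is censored early.

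The study is descriptive, so the tabulated numbers are the result. With 12 holiday and 29 control subjects enrolled (SAP 2.3), the product-limit median may not be reached. The flarers-only median would then be the only median in the table, and a reader could take it for the comparison.

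**Working it through.** The documents give no expected holiday-versus-control difference, so there is no design figure to reproduce. The flare rates in Protocol Table 4 (repeated in SAP 2) serve as 52-week risks, with placebo standing in for holiday and 10 mg/kg for control. Constant hazards and independent exponential dropout are assumptions.

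**1. Flarers-only day, equal 52-week windows, no dropout.** Weekly hazard l = -ln(1 - p)/52. True median = ln 2 / l. The flarers-only median t solves 1 - exp(-l t) = p/2.

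For p = 68.5%, l = 0.0222, so the true median is 31.2 weeks and the flarers-only median 18.9. For p = 57.5%, l = 0.0165, giving 42.1 and 20.6.

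| Holiday v control risk | True medians (weeks) | Gap | Flarers-only medians | Gap | Share of gap lost |
|---|---|---|---|---|---|
| 81.5% v 74.6% | 21.4 v 26.3 | 4.9 | 16.1 v 17.7 | 1.6 | 68% |
| 68.5% v 57.5% | 31.2 v 42.1 | 10.9 | 18.9 v 20.6 | 1.7 | 84% |
| 73.4% v 67.4% | 27.2 v 32.2 | 4.9 | 18.0 v 19.1 | 1.1 | 78% |

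**2. Flarers-only day, unequal windows.** Suppose the holiday group is summarised over its 24-week phase and control over 52 weeks. At 68.5% v 57.5% the flarers-only medians are 73 v 144 days, a gap of 71 days. With both groups at 52 weeks they are 132 v 144, a gap of 12; with both at 24 weeks, 73 v 76. The wide gap comes from the truncation.

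**3. Crude percentage.** With 52-week flare hazard a = -ln(1 - p) and dropout hazard b = -ln(1 - d), the expected crude proportion is a/(a + b) × (1 - exp(-(a + b))). True risks are 68.5% and 57.5%, a difference of 11.0 points. Dropout d is assumed.

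| Dropout holiday / control | Crude holiday | Crude control | Difference |
|---|---|---|---|
| 10% / 10% | 65.7% | 55.0% | 10.7 |
| 20% / 20% | 62.7% | 52.3% | 10.3 |
| 30% / 30% | 59.6% | 49.6% | 10.0 |
| 30% / 10% | 59.6% | 55.0% | 4.6 |
| 10% / 30% | 65.7% | 49.6% | 16.1 |

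The shortfall in each level runs from 57.5 - 55.0 = 2.5 to 68.5 - 59.6 = 8.9 points.

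**4. Whether the product-limit median is reached.** With no dropout it is not reached when fewer than half the group flare: at most 5 of 12, or at most 14 of 29. From the binomial distribution:

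| 52-week risk | n = 12 | n = 29 |
|---|---|---|
| 68.5% | 0.05 | 0.02 |
| 57.5% | 0.21 | 0.21 |
| 40% (assumed) | 0.67 | 0.86 |

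**5. The product-limit 52-week risk.** A simulation of 4,000 trials with 12 and 29 subjects, risks of 68.5% and 57.5% and 20% dropout in both groups gave a mean product-limit difference of 11.1 points (SD 17.7) and a mean crude difference of 10.4 (SD 16.8). With dropout of 30% holiday and 10% control the means were 10.7 and 4.4; reversed, 11.0 and 16.1. The product-limit figure stays near 11.0 throughout. One holiday subject is 1/12 = 8.3 points.

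**The case against.** The strongest reply is that the valid analysis is already there. The product-limit quartiles stand in the same table, and the cumulative incidence curve is a headline figure that handles censoring. The flarers-only line says whom it covers, and no test is affected. All of this stands, and it makes the point one of reporting. A reader might infer that only the two weak numbers remain when the median is not reached. That is wrong: the curve remains, and even at an assumed 40% risk the product-limit 25th percentile is reached with probability 0.92 (n = 12) and 0.94 (n = 29).

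A reader might also infer that both figures pull the comparison toward no difference. The documents do not support that. With equal dropout of 10% to 30% the crude difference loses at most 1 point; with unequal dropout it can shrink or inflate, and no dropout rates are given. The flarers-only gap shrinks on equal windows but can widen on unequal ones.

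Nor should the dropout argument be carried to Table 2.3 (severe flares). SAP 7.2.4.1 counts a withdrawal as a flare there, although it also refers back to the censoring rules of 7.1.4, and the table layout is not shown.

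Finally, the 40% risk is an assumption. Low-activity subjects may flare less often than the pooled trials suggest, but no document gives that figure.

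**Conclusion.** The point holds as a reporting weakness in the primary table. The flarers-only day is unsuitable for comparing groups: on equal 52-week windows it loses about 68% to 84% of the median gap at the plan's own rates, and it can overstate the gap if only the holiday group is truncated at Week 24. Each crude percentage understates the 52-week risk, by about 2.5 to 9 points at 68.5% and 57.5% risk with 10% to 30% dropout; the direction of error in the difference is unknown.

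These sizes rest on constant hazards, independent dropout, the ITT group as denominator, and pooled-trial rates as stand-ins. The sampling SD of the difference, about 17 points in the simulation, exceeds these errors, so the change makes the table answer the right question without making it precise.

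**What to change.** In SAP 7.1.5 and Table 2.1:

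- Add the product-limit cumulative flare probability at Week 24 and Week 52 per group, with numbers at risk, and use these as the reported flare percentages.
- Keep n with a flare, and label n/N as crude.
- Label the flarers-only study day as supplementary and not for group comparison. Deleting it is optional; flares remain in Listing 43.

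The Week 24 figure gives a like-for-like comparison at the end of the holiday, whatever window the phase-wise display uses. The estimates come from the fit already planned, so the cost is SAP wording and one table shell. If the flarers-only line is deleted, its minimum and maximum also leave the table.
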